11.5 Interim Analysis

There are no interim analyses planned as this is an open-label study; however, safety data will be reviewed by the SRC continuously throughout the study period. In addition to specific dose level reports, quarterly safety reports on all enrolled patients will be provided to the SRC during the study period. These reports will include summary tables overall and by cohort and site on baseline characteristics, treatment completions and reasons for early treatment withdrawals, study completions rates and all outcomes related to safety information including all adverse events and serious adverse events.

11.6 Statistical Analyses

Tables and listings will be produced using SAS v9.2 or higher (SAS, Cary, NC). Data summaries by cohort group will be presented. For continuous variables, data will be summarized with the number of patients, mean, standard deviation, median, and minimum and maximum overall and by cohort. For categorical variables, data will be tabulated in frequency tables to display the number and proportion of patients for each category overall and by cohort. Baseline assessments for each outcome variable will be defined as the last measurement obtained before treatment initiation. Each point estimate will be presented with 2-sided 95% confidence intervals and all statistical tests will use a two-sided 5% significance level.

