3.3.2 Rationale for Dose Selection

Ocera Therapeutics, Inc. (Durham, NC) has conducted two clinical trials evaluating safety, tolerability and pharmacokinetics in healthy volunteers (n=48) and stable cirrhotic patients (n=43).

Clinical study OCR-002 HE201 was designed as a randomized, placebo-controlled, dose-ranging study, evaluating doses (i.v. infusion) of 1, 3, 10, 20 and 30g given over 4h, and 30, 40 and 60g given over 24h. Following a single ascending dose phase, a multiple ascending dose phase (5d of consecutive administration) for doses of 1, 3, 10 and 20g given over 4h was assessed. The key findings in this study included:

There were no deaths, SAE or AE discontinuations in the study.

A dose related increase in the incidence and severity of adverse events was observed.

Commonly occurring adverse events that appeared to be related to dose included dizziness, somnolence, headache, nausea/vomiting and tinnitus.

There was no evidence to suggest that AEs increased or new AEs occur with multiple dosing.

With respect to blood pressure, there were no apparent trends from placebo with respect to mean changes from baseline; however at dose levels $\geq 20\text{g}/4\text{h}$, several patients experienced clinically significant orthostatic hypotension.

There appeared to be a dose and exposure related increase in mean heart rate starting at a dose level of $10\text{g}/4\text{h}$ and higher. These effects also persisted for longer periods in the higher dose groups.

20g administered over 4 h was the maximum tolerated dose (MTD), however, doses of $10\text{g}/4\text{h}$ and below were well tolerated.

24h Holter monitor recording identified a dose-related increase in heart rate accompanied by modest effects on ventricular repolarization as measured by QT. These effects should be interpreted with caution in light of the small sample size and higher heart rates observed in this study.

There were no clinically significant abnormal laboratory parameters and no patient had any clinically significant changes in physical examination findings or mean

change in body weight between baseline and follow up.

Doses higher than 10g/4h are associated with adverse effects that may be rate and C_{max} related and are likely associated with the non-linear pharmacokinetic profile of phenylacetate above 10 g.

A slower infusion rate (24hr-infusion) avoids C_{max} related adverse effects while providing similar excretion of PAGN.

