11.7.5 Physical Exams

Physical examination findings at baseline will be listed. Clinically significant changes will be recorded as AEs. Symptoms of interest previously reported with OCR-002 will be recorded daily, including dizziness, headache, nausea, vomiting; daily monitoring of heart rate in relation to infusion initiation will also be recorded.

11.7.6 Plasma Ornithine, Phenylacetate, Phenylacetylglutamine and Glutamine Concentrations and Pharmacokinetic Parameters

Individual and mean plasma ornithine, phenylacetate, and PAGN concentrations at each sampling time point will be presented by listings and descriptive summary statistics. Plasma ornithine, phenylacetate, and PAGN concentration versus time profiles will be plotted.

In addition, individual and mean cumulative urinary PAGN output will be listed with descriptive statistics in tabular format.

Pharmacokinetic parameters will be calculated from plasma ornithine, phenylacetate, and PAGN. Individual plasma ornithine, phenylacetate, and PAGN parameters will be listed for each patient and summary statistics will be provided.

The following PK parameters will be calculated or derived from the data:

- Maximum observed plasma concentration (C_{max});
- Concentration at steady state (C_{ss});
- Clearance at steady state (CL_{ss}); and
- Interval estimates of exposure (e.g. AUC_{0-24h}) over multiple dosing days.

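### PK parameters fall under a generic arithmetic mean, SD and 95% interval rule, with no log-scale summary and with dose levels pooled within cohort (minor)

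*Combined protocol and SAP*

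**What the plan says.** Section 11.6 gives a single rule for continuous variables: the number of patients, "mean, standard deviation, median, and minimum and maximum overall and by cohort". It adds "Each point estimate will be presented with 2-sided 95% confidence intervals" and does not say how the interval is to be computed. Section 11.2 likewise plans evaluation overall and by cohort. Nothing in Section 11 plans final summaries by dose level.

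For PK, Section 11.7.6 adds this: "Individual and mean plasma ornithine, phenylacetate, and PAGN concentrations at each sampling time point will be presented by listings and descriptive summary statistics". It also asks for concentration-time plots and cumulative urinary PAGN output with descriptive statistics. For the derived parameters (Cmax, Css, CLss and interval AUC such as AUC0-24h), it says that individual "parameters will be listed for each patient and summary statistics will be provided". No geometric mean, geometric CV or log transformation is mentioned anywhere. The closing memorandum states that no separate SAP was compiled, so no later document fills the gap.

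**The concern.** Concentrations, exposures, clearances and urinary outputs cannot be negative, and variation between patients in such quantities is often closer to multiplicative than additive. If so, a few high-exposure patients pull the arithmetic mean up, and an interval symmetric about that mean does not have its nominal coverage. Its errors fall mainly on one side: the whole interval tends to sit below the true mean and so understates average exposure.

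A second difficulty comes from the grouping. Each cohort contains patients treated at about 3.33, 6.65, 10 and 20 g/24h. One cohort mean for a quantity that scales with dose then describes the mix of doses as much as the drug's behaviour in that renal group.

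What is at stake is how well the reported PK summaries describe exposure, which is a secondary objective. No hypothesis test or decision threshold depends on them.

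**Working it through.** The plan states no precision or coverage figure for PK, so there is none to reproduce.

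**Inputs from the documents**
- Reporting groups: overall, up to 36 evaluable; by cohort, about 18 each (Sections 5.1, 11.2, 11.6).
- Dose levels: 3.33, 6.65, 10 and 20 g/24h (Section 5.2).
- Evaluable patients: up to 24 at Levels 1 to 3 and up to 12 at Level 4 (Section 3.3.2). Three per cohort are planned at each of Levels 1 and 2, and at least three at Level 3 (Section 5.1).

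**Assumptions**
- Log-normal data within a dose level, shown over a range of CV because the documents give none.
- An ordinary t-interval, because Section 11.6 names no method.
- For pooled calculations, 3, 3, 6 and 6 patients at Levels 1 to 4 in a cohort of 18 (the totals above split evenly between cohorts), with exposure proportional to dose.

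**Step 1: coverage at n = 18, single dose level.** The interval is mean ± t(0.975, 17) × SD/√18. Simulated coverage of the true arithmetic mean (100,000 samples per setting):

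| CV | Coverage |
|---|---|
| 40% | 0.938 |
| 60% | 0.924 |
| 80% | 0.908 |
| 100% | 0.891 |

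At CV 80% the whole interval lies below the true mean in 8.8% of samples and above it in 0.4%, against a nominal 2.5% on each side. At n = 36 the shortfall is smaller: 0.939 at CV 50% and 0.911 at CV 100%.

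**Step 2: can the lower limit be negative?** It is negative exactly when the sample CV exceeds √n / t(0.975, n−1). That threshold is 40% at n = 3, 95% at n = 6, 201% at n = 18 and 296% at n = 36. At n = 18 this happened in about 0.3% of samples at CV 100%, and essentially never at CV 70% or below.

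**Step 3: effect of pooling doses.** Sum of doses in the assumed cohort: 3×3.33 + 3×6.65 + 6×10 + 6×20 = 209.94, so the mean is 209.94/18 = 11.66. Level 4 supplies 120/209.94 = 57% of it. Dose alone produces a CV of about 56%, before any variation between patients. Coverage of the t-interval for the pooled cohort mean is 0.998 at within-dose CV 30%, 0.977 at 50%, 0.946 at 70% and 0.903 at 100%. At low CV it over-covers, because the fixed spread between doses inflates the SD without being sampling error.

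**Step 4: the log-scale alternative.** Take logs, form the t-interval and back-transform. Within one dose level its coverage of the geometric mean is 0.95 at every n tested (3, 6, 18, 36) and every CV from 30% to 150%, and its lower limit is always positive. The median ratio of upper to lower limit at n = 18 is 1.58 at CV 50% and 2.25 at CV 100%. At n = 3 it is 7.0 and 31, which is valid but hardly informative. Applied to the pooled cohort, the log-scale interval covers 0.975 to 1.000 over CV 30% to 150%, so changing the scale does not cure the pooling.

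**The case against.** The strongest reply is that this is a reporting convention. The study is descriptive and not powered, no PK test is planned, and the skewness is assumed. At CV 40% to 60% the shortfall is only one to three percentage points. Section 11.6 already provides the median, minimum and maximum, and Section 11.7.6 provides individual values and plots, so high-exposure patients will be visible. The unspecified summary statistics in 11.7.6 do not exclude geometric ones. All of this stands and limits the point to a minor one. It does not supply an interval method or repair the interval that Section 11.6 requires.

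A reader might also infer stronger claims that the documents do not support:

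- **Negative confidence limits in the planned tables.** These are a real risk at n = 3 or 6, but Section 11 plans tables overall and by cohort, where step 2 shows they are rare.
- **Distorted dose-escalation decisions.** Section 9.7 says the SRC reviews safety and PK data supplied by the SDCC, but nowhere that it receives mean-based intervals for groups of three. The escalation and stopping rules in the synopsis and Section 9.7.1 count graded SAEs, not PK limits.
- **Documented skewness.** Section 3.3.2 mentions a "non-linear pharmacokinetic profile of phenylacetate above 10 g", but in connection with doses above 10 g over 4 h, which is 10/4 = 2.5 g/h. The highest rate here is about 0.83 g/h. Non-linearity with dose is also not evidence of skew within a dose.
- **Pooling makes under-coverage worse.** Step 3 shows that it can reverse it.

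**Conclusion.** The point holds as a minor reporting improvement. By default the PK parameters and urinary PAGN output would receive an arithmetic mean, SD and 95% interval, with no log-scale summary and no stated method. Under log-normality and a t-interval, coverage at about 18 per cohort falls short of 95% by about 1 point at CV 40% and 6 points at CV 100%, mostly through intervals lying below the true mean. Those figures apply to data from one dose level, or to a quantity that does not depend on dose. For Cmax, Css and AUC pooled over Levels 1 to 4, the larger problem is interpretation: a cohort mean drawn from a sixfold dose range describes no dose that was given. The size rests on an assumed CV, distribution, interval method and dose mix. The absence of a log-scale summary and of a by-dose PK presentation rests on the text alone.

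**What to change.** In Section 11.7.6, state that Cmax, Css, CLss, AUC0-24h and urinary PAGN output will also be summarised by geometric mean and geometric CV%, with 95% intervals computed on the log scale and back-transformed, next to the median and range. Present these by dose level within cohort, or dose-normalised. CLss may be summarised by cohort if clearance does not depend on dose. Where a cell holds about three patients, rely on individual values, median and range. State how zero or unquantifiable values are handled, since they have no logarithm.

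The cost is a few sentences, simple programming and some extra table rows, with no new data. The drawback is that intervals in small cells will be wide.

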Study Design Continued	
to obtain 36 evaluable patients. Dosing with OCR-002 may be initiated immediately after obtaining signed informed consent; or, up to 32 h after obtaining consent should the time be necessary to complete any pre-study drug initiation requirements and/or to provide a time frame for study drug administration.
 
Baseline is immediately prior to the start of the initial infusion. At Treatment Day 1 - Time “0” (T0) and after baseline measurements, patients enrolled at Dose Levels 1 through 3 will receive an initial infusion rate of OCR-002. Dose will be escalated to a maximum dose of 10g/24h infusion as indicated herein. Patients receiving Dose Level 4 will receive the full 20 gm/24 hour dose level from initiation of infusion for a maximum time of 120 hours with no further dose escalation, provided the dose level is well tolerated with no noteworthy side effects. Titration of dose will depend on evidence of safety and tolerability (refer to Treatment section below).
 
Patients may have an IV catheter inserted as a safer and easier method for obtaining repeated blood sampling and a separate IV for the infusion. Blood samples for measurement of plasma ornithine, phenylacetate and PAGN concentrations will be collected at multiple time-points during the infusion period, at the Completion of the Last Infusion and up to 24 hours Following the Completion of the Last Infusion. Urine will be collected at specific intervals to determine the amount of PAGN excreted.
 
Patients will be assessed for safety and tolerability of OCR-002 as well as pharmacokinetic and pharmacodynamic variables during the infusion period, at the Completion of the Last Infusion and 24 hours Following the Completion of the Last Infusion. Data on clinical outcomes will also be collected during the study period.
 
Safety data will be reviewed by a Safety Review Committee (SRC) operating under an approved charter and made up of three ALFSG clinicians who are independent of the participating clinical sites and a clinical pharmacologist with experience in PK and clinical trials. Throughout the trial, the SRC will review all safety data at regular intervals, and the FDA will receive annual IND reports.
 
Supportive Care
 
Inotropic support may be used to maintain mean arterial pressure above 65 mm Hg in patients who are hypotensive either before or after enrollment. Dialysis or continuous veno-venous hemofiltration (CVVH), endotracheal intubation and mechanical ventilation will be considered as indicated. Cerebral edema will be managed post-enrollment with mannitol or hypertonic saline per local institutional practices. Antibiotic therapy may be initiated and modified as required. In patients who have intracranial pressure (ICP) monitors placed, ICP, cerebral perfusion pressure and mean arterial pressure will be recorded continuously and reported hourly.

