Study	Up to 36 evaluable male and female patients aged 18 to 65 years (have not reached

Population	their 66th birthday) with acute liver failure or severe acute liver injury will participate.
Key Inclusion Criteria	
 1. Men and women, ages 18-65 (have not reached their 66th birthday). 2. Acute liver failure, defined as the development of coagulopathy (International normalized ratio [INR] ≥ 1.5) with encephalopathy in a patient with no prior history of liver disease with onset of symptoms within 28 days of the inciting event. Patients may have either a history of acetaminophen overdose (defined as >4 g/day within 7 days of presentation) and/or detectable acetaminophen levels in the serum, with a pattern of liver function tests typical for acetaminophen toxicity (bilirubin < 10 mg/dL and alanine aminotransferase (ALT) ≥ 1000 IU/L), or a diagnosis of hepatitis A, hepatitis B, drug-induced liver injury, autoimmune hepatitis or indeterminate cause based on standard criteria; refer to Section 6.2.1 for the definitions of standard criteria for these diagnoses. 3. ALI patients may also be enrolled (those meeting the above criteria plus coagulopathy (INR ≥ 2.0) and no evidence of encephalopathy and may provide consent themselves. 4. Written informed consent from the patient or patient's legally authorized representative or family member as defined in 21CFR50.3(m)--if he/she has evidence of encephalopathy (ALF). 5. Ammonia level ≥ 60 μmol/L at baseline (within 8 hrs prior to infusion start time). 6. Serum creatinine levels as follows: 
 a. Cohort 1: Creatinine ≤ 1.5 mg/dL; and b. Cohort 2: Creatinine >1.5 mg/dL and < 10 mg/dL. 7. Mean arterial pressure of >65 mmHg.

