4 OBJECTIVES AND ENDPOINTS

4.1 *Objectives*

4.1.1 **Primary Objective**

To evaluate the safety and tolerability of OCR-002 in patients with acute liver failure/severe acute liver injury.

Hypothesis: Treatment with OCR-002 is safe and tolerable in patients with acute liver failure/acute liver injury.

4.1.2 **Secondary Objectives**

To evaluate the steady state pharmacokinetic and pharmacodynamic profile of OCR-002 in patients with impaired and minimal renal dysfunction using urinary PAGN as a surrogate marker.

Hypothesis: A dose of 10-20g/24h (0.42-.83g/h) will achieve steady state plasma concentrations within 6-12h with little additional accumulation in the ALI/ALF setting.

To evaluate the effect of OCR-002 on ammonia levels in patients with acute liver failure/severe acute liver injury.

Hypothesis: Treatment with OCR-002 will reduce ammonia levels in patients with ALI/ALF.

To evaluate the effect of OCR-002 on neurological function in patients with acute liver failure/severe acute liver injury.

Hypothesis: Treatment with OCR-002 will improve neurological function in patients with acute liver failure/severe acute liver injury.

4.2 *Endpoints*

4.2.1 **Safety Endpoints**

Safety assessments will include: abbreviated physical examinations, vital signs (blood pressure, pulse rate, respiration rate, and body temperature), clinical laboratory tests (hematology and serum chemistry), 12-lead ECGs, and reported and observed adverse events.

4.2.2 **Exploratory Efficacy Endpoints**

- Ammonia concentrations.
- Neurological assessment will be measured by the Glasgow Coma Scale, the West Haven Criteria, and the Orientation log (O-log) (34).

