5 INVESTIGATIONAL PLAN

5.1 *Study Design*

This is a Phase 2a, multi-center, open-label study, conducted in two cohorts in patients

diagnosed with acute liver failure/severe acute liver injury (ALF/ALI) who meet inclusion/exclusion criteria. The acetaminophen adduct assay will be used as an additional test for equivocal or presumed cases of acetaminophen toxicity, where the history is not substantiated and the assay for acetaminophen itself proves to be negative.

Up to 36 evaluable patients are planned to be enrolled in two cohorts:

Cohort 1 will include patients with ALF/ALI with minimal renal dysfunction at the time of enrollment (defined as serum creatinine ≤ 1.5 mg/dL and mean arterial pressure of >65 mmHg).

Cohort 2 will include patients with ALF/ALI with compromised renal function (defined as a serum creatinine >1.5 mg/dL and <10 mg/dL) and mean arterial pressure of >65 mmHg.

Informed consent will be obtained from the patient and/or patient's legally authorized representative or family member [as defined in 21CFR50.3(m)]. All patients will receive medical care for acute liver failure/severe acute liver injury according to the institution's standards of care. Standard of care may include, but is not limited to, administration of NAC and consideration for orthotopic liver transplantation. All patients in Cohort 2 with a serum Cr level of ≥ 2.0 will be considered for placement on continuous veno-venous hemodialysis (CVVHD) for an appropriate interval as standard of care for this condition.

The initial dose of OCR-002 will be initiated once consent is obtained, all eligibility criteria are confirmed to be met and all baseline measurements have been completed. The infusion may begin after obtaining signed informed consent; or, up to 32 h after obtaining consent should the time be necessary to complete any pre-study drug initiation requirements and/or to provide a time frame for study drug administration.

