6.2 Selection Criteria

6.2.1 Inclusion Criteria

1. Men and women, ages 18-65 (have not reached their 66th birthday).
2. Acute liver failure, defined as the development of coagulopathy (International normalized ratio [INR] ≥ 1.5) with encephalopathy in a patient with no prior history of liver disease, with onset of symptoms within 28 days of the inciting event. Patients may have either a history of acetaminophen overdose (defined as >4 g/day within 7 days of presentation) and/or detectable acetaminophen levels in the serum, with a pattern of liver function tests typical for acetaminophen toxicity (bilirubin < 10 mg/dL and alanine aminotransferase (ALT) ≥ 1000 IU/L), or a diagnosis of hepatitis A, hepatitis B, drug-induced liver injury, autoimmune hepatitis or indeterminate cause based on standard criteria. Standard criteria for these diagnoses are as follows:
 - hepatitis A, defined as positive anti-HAV IgM;
 - hepatitis B, defined as positive anti-HBc IgM and positive HBsAg;
 - autoimmune hepatitis, defined as follows:
 - Globulins elevated $> 1.5X$ ULN;
 - ANA, ASMA or LKMA positive in titer of at least 1:80;
 - Negative serology for viruses associated with acute or chronic hepatitis; and/or

- Liver biopsy showing CAH;
- drug-induced liver injury, defined as presumed injury by a likely agent, with other causes excluded; or
- indeterminate cause, defined as
 - the exclusion of all the diagnoses listed in the Selection Criteria (see Section 6.2), including:
 - Budd-Chiari;
 - Hepatitis C, E, delta, drug-induced hepatitis;
 - mushroom intoxication; and
 - other viruses, defined as follows:
 - HSV: anti-HSV IgM positive and anti-HSV IgG negative and four fold increase between acute and convalescent sera and HSV seen in liver tissue;
 - EBV: anti-EBV IgM or EBV seen in liver tissue; and
 - CMV: anti-CMV IgM positive and anti-CMV IgG negative and four fold increase between acute and convalescent sera or CMV seen in liver tissue.

3. ALI patients may also be enrolled (those meeting the above criteria plus coagulopathy (INR \geq 2.0) and no evidence of encephalopathy).
4. Written informed consent from the patient (ALI) or patient's legally authorized representative or family member if he/she is considered encephalopathic (ALF).
5. Ammonia level \geq 60 μ mol/L at baseline (within 8h prior to T0/initiation of infusion).
6. Serum creatinine levels as follows:
 - a. Cohort 1: Creatinine \leq 1.5 mg/dL; and

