8.1 Screening

Patients will be evaluated for entry into the study according to the stated inclusion and exclusion criteria. Individuals who are identified during screening as not eligible for the study need not complete all screening procedures. The reason for ineligible status will be documented on the Screen Failure Log.

The following procedures will be obtained or performed to evaluate each patient's general health and qualifications for participation in the study:

- Demographic information including gender, date of birth, race and ethnicity;
- Medical and medication history over the past 30 days, including prescription and non-prescription over-the-counter medications, herbal medications, vitamins, and minerals;
- Collection of blood for hematology, coagulation, clinical chemistry, ammonia* and in female patients, a pregnancy test**;

*** Venous sampling is the protocol-preferred method of collection for ammonia samples. Arterial ammonia samples will be accepted if this is the available method; however, this same method should be used for all subsequent ammonia samples for the patient.**

**Urine pregnancy test or blood human chorionic gonadotropin (hCG) is acceptable.

- Urinalysis***;
 - ***Urinalysis: dipstick plus microscopic evaluation of sediment, if clinically indicated.
- Physical examination, including height and weight (body mass index will be calculated based on these variable), and vital signs (systolic and diastolic blood pressure, pulse rate, respiratory rate, body temperature);
- 12-lead ECG;
- Neurological battery, including
 - Glasgow Coma Scale;
 - West-Haven Scale; and
 - O-Log Scale;
- Review inclusion and exclusion criteria; and
- Signed, written informed consent.

The start of the initial infusion may begin after obtaining signed informed consent; or, up to 32 h after obtaining consent should the time be necessary to complete any pre-study drug initiation requirements and/or to provide a time frame for study drug administration. Patients will be considered enrolled once the informed consent has been obtained, all eligibility criteria have been met, and the study drug infusion initiated.

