8.2 Assessments at Baseline

- Collection of blood for hematology, coagulation, clinical chemistry, ammonia* and PK*;

***The ammonia and plasma PK samples must be taken not more than 8 hours prior to the start of the initial study drug infusion. Venous sampling is the protocol-preferred method of collection for ammonia samples. Arterial ammonia samples will be accepted if this is the available method; however, this same method should be used for all subsequent ammonia samples for the patient.**
- Vital signs and abbreviated physical exam;
- Neurological battery**, including
 - Glasgow Coma Scale;
 - West-Haven Scale; and
 - O-Log Scale;

****Neurological exams at the Baseline visit should be performed within 8 hours prior to the start of the initial study drug infusion.**
- 12-lead ECG;***

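### The ammonia value that qualifies a patient can also be the analysis baseline, so in this single-arm trial the change from baseline carries a regression-to-the-mean fall

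*Combined protocol and SAP*

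**What the plan says.** - **Eligibility.** Criterion 5 (synopsis and section 6.2.1) sets the threshold, "Ammonia level ≥ 60" µmol/L, and applies it "at baseline (within 8h prior to T0/initiation of infusion").
- **Sampling.** Section 8.1 lists a screening draw: "Collection of blood for hematology, coagulation, clinical chemistry, ammonia* and in female patients, a pregnancy test". Section 8.2 lists a second draw at baseline: "The ammonia and plasma PK samples must be taken not more than 8 hours prior to the start of the initial study drug infusion".
- **Analysis baseline.** Section 11.6: "Baseline assessments for each outcome variable will be defined as the last measurement obtained before treatment initiation".
- **Timing.** The synopsis (Study Design) says: "Baseline is immediately prior to the start of the initial infusion". This does not match the 8 h allowed in section 8.2.
- **Design and hypothesis.** Section 5.1: "This is a Phase 2a, multi-center, open-label study, conducted in two cohorts". Every patient receives OCR-002. Under a secondary objective, section 4.1.2 states: "Treatment with OCR-002 will reduce ammonia levels in patients with ALI/ALF". Section 4.2.2 lists ammonia among the exploratory efficacy endpoints.
- **Analysis.** Section 11 has no subsection on ammonia. Section 11.6 attaches 95% confidence intervals to point estimates and sets a two-sided 5% level for any test. No replicate baseline, adjustment or external reference is given for ammonia.

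**The concern.** The threshold in criterion 5 acts on the baseline value, and the baseline value is the reference for change. Some patients pass because their ammonia happened to be high when sampled. Their later values tend back towards their own usual level, and this appears as a fall after treatment starts. In a randomised trial both arms would share the effect and the comparison would remove it. Here nothing does.

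At stake is the reading of the secondary ammonia hypothesis, which is directional. Section 3.3.1 expects this study to lead on to a development programme in hyperammonaemia, so a mean fall with an interval that excludes zero could carry weight. The primary safety objective is not affected.

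**Working it through.** **Which sample is which.** There are two routes.
1. The section 8.2 baseline draw is tested against criterion 5. It is normally also the last pre-dose value, so it is the analysis baseline. Selection and reference coincide.
2. A screening draw that falls within 8 h of T0 is used to qualify the patient, and a later baseline draw follows. That later draw becomes the analysis baseline and has not been selected on.

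Criterion 5 names baseline, which favours route 1. Route 2 is possible but not required.

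**Size.** The plan gives no figure to reproduce: it states no ammonia mean, SD, within-patient correlation or expected effect. The inputs below are therefore assumptions, apart from the threshold of 60.

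Take ammonia as normal before selection with mean m and standard deviation SD, correlation ρ between two samples, no drug effect and no time trend. With a = (60 − m)/SD and λ = φ(a)/(1 − Φ(a)):

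- selected mean = m + SD × λ
- expected fall = (1 − ρ) × SD × λ

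Corners of the grid m 80 to 110, SD 40 to 50, ρ 0.5 to 0.85:

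| m | SD | a | λ | Selected mean | Fall, ρ = 0.5 | Fall, ρ = 0.85 |
|---|---|---|---|---|---|---|
| 80 | 40 | −0.50 | 0.509 | 100.4 | 10.2 | 3.1 |
| 80 | 50 | −0.40 | 0.562 | 108.1 | 14.1 | 4.2 |
| 110 | 40 | −1.25 | 0.204 | 118.2 | 4.1 | 1.2 |
| 110 | 50 | −1.00 | 0.288 | 124.4 | 7.2 | 2.2 |

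- Largest: 0.5 × 50 × 0.562 = 14.1 µmol/L; 14.1/108.1 = 13%.
- Smallest: 0.15 × 40 × 0.204 = 1.2 µmol/L; 1.2/118.2 = 1%.

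Outside this grid the result moves a long way. With m = 150 and SD 30 the fall is below 0.1 µmol/L. With m = 60, SD 50 and ρ = 0.5 it is 20.

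**Effect on a test, if one were done.** A paired t-test at two-sided 5% was simulated with no drug effect (4,000 trials per setting). The nominal rate of significant falls is 2.5%.

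| Setting | ρ = 0.5 | ρ = 0.7 | ρ = 0.9 |
|---|---|---|---|
| Normal, mean 80, SD 50, n = 36 | 43% | 26% | 10% |
| Normal, mean 80, SD 50, n = 18 | 24% | 15% | 7.5% |
| Lognormal, median 80, log-SD 0.5, n = 36 | 16% | 9% | 5% |
| Normal, mean 150, SD 50, n = 36 | about 4% | about 4% | about 4% |

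**Effect of separating the samples.** Simulation with SD 50, means 60 to 120, ρ 0.5 to 0.9 and n = 36 used a second pre-dose sample, not used for selection, as baseline. The artificial fall was about 0 (mean change −0.2 to +0.1 µmol/L), with significant falls in 2.3 to 3.0% of trials. This assumes that fluctuations are independent between samples.

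**Effect of averaging.** If the qualifying value is averaged with an unselected one, the baseline excess is (1 + ρ)/2 × SD × λ. The follow-up excess is ρ × SD × λ. The fall is then (1 − ρ)/2 × SD × λ, exactly half. For m = 80, SD 50 and ρ = 0.5 it drops from about 14 to 7 µmol/L.

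**The case against.** The strongest case against is that the point has little consequence. The synopsis says the study lacks power for significance testing, the analysis is descriptive, and ammonia is an exploratory endpoint. No ammonia change score is written out: the explicit change-from-baseline text covers laboratory tests, vital signs and ECG (sections 11.7.2 to 11.7.4). Without a control, the course of the illness already prevents attributing a fall to the drug, and so does a primary analysis set limited to patients with at least 72 h of infusion. This stands as a reason to keep the point in proportion. It does not remove the bias from a descriptive mean and interval that bear on a stated directional hypothesis.

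Three stronger readings are tempting, and the documents do not support them.
- *A net fall is guaranteed.* Only the regression component has a fixed sign. Section 3.1 describes ammonia in acute liver failure as tending to climb quickly, which would work against a net fall.
- *The 8 h age of the sample adds favourable bias.* Sample age does not cause regression to the mean. If ammonia is rising, an older baseline understates the level at T0 and works against the drug. The mismatch between the synopsis and section 8.2 is a separate timing inconsistency.
- *The qualifying sample and the baseline are always the same.* The screening draw makes separation possible. The plan simply does not require it.

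**Conclusion.** The point holds in a limited form. The plan does not ensure that the qualifying ammonia value and the analysis baseline are separate samples, and it has no control arm. The ammonia change from baseline therefore contains a regression-to-the-mean component in the direction of a fall whenever the correlation between samples is below 1 and the qualifying value is the reference.

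Under the assumed grid the component is about 1 to 14 µmol/L (1 to 13% of the selected mean). The documents cannot say where in or outside that range the trial lies. The size depends mainly on how many screened patients sit near 60 µmol/L, and it is trivial if most lie far above. The change is worth making because it is cheap and the ammonia result is meant to inform later development.

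**What to change.** 1. In criterion 5 (synopsis and section 6.2.1) and in sections 8.2 and 11.6, state that eligibility is judged on one ammonia sample, for example the screening draw. State that a separate later pre-dose sample, not used for eligibility and taken as close to T0 as possible, is the analysis baseline. Criterion 5 must be reworded because it now tests the baseline value. The new text should say which sample its 8 h limit refers to, since sections 7.4 and 8.1 allow up to 32 h from consent to infusion.
2. Reconcile the synopsis definition of baseline with the 8 h window in section 8.2.
3. Where screening and baseline values both exist but the baseline value qualified the patient, report their mean as a sensitivity baseline, labelled as a partial correction. It is not available where only one sample exists.
4. State in the report that an uncontrolled fall from baseline is not by itself evidence of drug effect.

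Cost: at most one extra blood tube per patient and short text edits. Some bias remains if fluctuations persist from the first sample to the second. If sampling is already complete, items 3 and 4 can still be done.
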